The study will be conducted at the academic medical center, specifically the Clinical Research Unit (CRU) of the Wake Forest School of Medicine (WFSM) and with the support of the Pepper Center and Translational Science Institute. The participants will be recruited from the general community and evaluated and followed by the CRU.

Subjects selection criteria

Elderly at risk for disability with mild impairment of kidney function will be selected for this study.

Inclusion Criteria	Exclusion Criteria
Age 65+ years of age	Uncontrolled (>160 mg/dl fasting blood glucose), insulin-dependent diabetes and/or uncontrolled hypertension (SBP >160 , DBP >100)
SPPB (short physical performance battery) score >3	a current diagnosis of psychotic disorder or taking anti-psychotic medication
eGFR stage 2 (60-89) or 3 (30-59)	take more than 14 alcoholic drinks per week
	plan to relocate out of the study area within the 8 months
Net endogenous acid production (NEAP) >40 mEq/d	self-reported inability to walk across a room
Willing to provide informed consent and agrees to randomization	those who reside in nursing homes
Not involved in another intervention study	have difficulty communicating with study personnel due to speech or language or hearing problems
	had cancer requiring treatment in the past 1 year
	lung disease requiring regular use of corticosteroids at a dose of >7.5 mg/d for the last 3 months or use of supplemental oxygen
	cardiovascular disease (Class III or IV congestive heart failure)
	significant valvular disease, uncontrolled angina
	myocardial infarction, major heart surgery (i.e., valve replacement or bypass surgery) in past 6 months
	stroke, deep vein thrombosis, or pulmonary embolus in the past 6 months,
	Parkinson's disease or other progressive neurological disorder
	other medical or behavioral factors that in the judgment of the principal investigator may interfere with study participation or the ability to follow the intervention
	clinical judgment concerning safety or noncompliance
	Individuals with BMI <18.5 ; or unintentional weight loss $>4\%$ in last 6 months
	MoCA score under 24
	End Stage Renal Disease (ESRD) on dialysis or primary kidney disease
	Other illness of such severity that life expectancy is less than 12 months
	Any tobacco or nicotine product use in the past year
	Serum HCO ₃ >30 meq/L; serum K ⁺ out of normal range <3.5 or >5.2

Sample Size

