Oral bicarbonate supplementation group. Participants will be advised to continue their usual dietary and exercise pattern, but to take supplementation capsules. They will receive 0.3 meq/kg/day NaHCO₃, a dose based on the literature (14) and our Health ABC cohort preliminary study (8). The dose of 0.3 mg/kg/d NaHCO₃ was reported to reduce net acid excretion ~50% in individuals with similar daily acid load(14), and was effective in decreasing the rate of yearly eGFR decline in patients with hypertensive nephropathy; the dose has also been reported as safe (14, 15). NaHCO₃ will be provided in gelatin capsules containing 10 meq NaHCO₃, so that NaHCO₃ can be dosed to the nearest amount by total body weight; e.g, a 70kg person will receive 2 capsules daily, and an 85kg person would receive 3 capsules daily (14). Adherence will be assessed by pill count. Compliance will be measured at months 3 and 6 by determining the change from the baseline in net acid excreted (NEA) in 4hr-urine; an advantage of our approach is that compliance can be measured objectively rather than estimated. Oral bicarbonate has been used for decades in patients with CKD or distal renal tubular acidosis to treat metabolic acidosis(7), and is generally considered free from significant side effects. Participants will be withdrawn if any of the following occur: total carbon dioxide >30mmol/L, serum K+ <3.5mEq/L, hospitalization for congestive heart failure, weight gain >2kg due to edema, or increase in blood pressure (>15 mmHg systolic or diastolic) (7, 15).

Placebo group. Participants will be advised to continue their usual dietary and exercise pattern, but to take supplementation capsules (methylcellulose). To ensure participants' blinding, identical capsules will be taken and the total number of capsules kept constant. The placebo group will be followed in the same manner as the bicarbonate group; all assessors will be blinded with respect to group assignment.

Clinical assessments, laboratory analysis and analytical tests.

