Metabolomics. Metabolomics analysis of the urine samples collected at baseline and the last follow up visit will extend our preliminary findings: 1) to elderly individuals; 2) will test the predictive value of identified metabolites with targeted metabolomics and 3) will repeat the broad spectrum analysis in samples taken before and after the intervention, circumventing the uncertainty of the preliminary data, which relied on statistical associations. All analyses will be overseen by the Wake Forest School of Medicine Proteomics and Metabolomics Core (see the letter from the Director, [name]); the metabolomics samples are processed in collaboration with NIH Eastern Metabolomics Core at RTI170-74. We will use targeted metabolomics and broad spectrum ¹H NMR spectroscopy.

The copy of **the questionnaire** that will be used during the **initial phone call** to determine initial eligibility (e.g. to exclude individuals with already high consumption of fruits and vegetables (base-forming foods) or those meeting exclusion criteria based on medical history (self-reported insulin-dependent diabetes, advanced heart disease, end stage renal disease) are included in the protocol application. The **questionnaires** that will be used during **follow up telephone call and follow up visits** to evaluate safety and adherence and to collect 24hr-food recall data are also included.

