collection of these data throughout the study. The first recall will be conducted at the SV to review all procedures and tools to be used. A “Food Amounts” booklet containing 2-D visual portions will be provided to the participant for use in standardizing portion sizes. Subsequent recalls will be conducted by telephone with trained interviewers from the CRU placing unscheduled telephone calls to participants at seven additional timepoints. When contacted by the staff, subjects will be asked to recall and report their dietary intake from the previous day’s 24-hour period. In addition to the first in-person SV recall, telephone recalls will be done within one week of the SV (1) to further assess eligibility (an average of both protein intake and K+ will be used to calculate the NEAP score), and within a 1-week period of each follow-up visit for a total of eight recalls during the study. Recalls will be randomly scheduled and will reflect both weekday and weekend intakes.

At the baseline visit and remaining in-clinic follow up visits, participants will spend approximately 4hr in the Clinical Research Unit (CRU), have their physical ability tested (FV2 and FV3 only), have blood drawn for blood gas analysis as well as blood for cystatin c and blood for storage. The blood gas draw will be performed in the CRU. Urine will be collected over the 4hr period (this is necessary because urine collections need to be monitored and refrigerated). Participants will be encouraged to take 500 ml of water during their stay at the CRU, to stimulate urine production. During these visits (not at FV2) the participants will also provide information about their dietary habits using the VioFFQ™ (Viocare, Inc., Princeton, NJ), which is a validated, web-format system for collecting food frequency data on a subject’s dietary behavior and food use patterns. The questionnaire will be self-administered. Participants will also receive a DXA scan of their hip at BV and FV3.

Table showing Study Schedule of events	SV	BV	FV1	FV2	FV3
Location of Visit	CRU	CRU	Phone Call	CRU	CRU
Study Week Number Activity/Assessment	-1 wk	0	1 mo	3 mo	6 mo
Informed Consent	X				
Cognitive Screen (MoCA)	X				
Fasting blood draw (CMP)	X			X	X
Urinalysis (Spot Urine)	X				X
SPPB	X			X	X
400m walk test		X		X	X
VITALS	X	X		X	X
DXA		X			X
24-hour Diet Recall to calculate NEAP	X		X	X	X
Medical History and Medications	X		X	X	X
Food Frequency		X			X
Blood Gas, Cystatin C, blood for storage		X			X

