Shortness of breath	4 (20)	1 (5)	1 (5)	3 (15)	2 (11)	0.97
Hospitalization	0	0	0	0	0	—

Data are expressed as number (%). Data are presented for all 20 participants at each time point except for the 1.0-mEq/kg per day dose, when 18 participants remained in the study.

- 4) **Increased risk of cardiovascular disease.** Lower all-cause mortality has been reported for individuals with serum bicarbonate >23 mmol/L vs. <23 mmol/L. A recent study however reported slightly higher risk of heart failure in kidney patients with serum bicarbonate >24 mmol/L. Serum bicarbonate >24 mmol/L did not however associate with any increase in mortality or ischemic events in the same group of patients (25). As an additional precaution, we will calculate bicarbonate deficit (if any) for each individual (=serum bicarbonate x 50% body weight (kg)) to help adjust dosing regimen and will monitor serum bicarbonate after the initiation of the intervention to adjust the amount of bicarbonate administered, if needed.
- 5) **Predisposition to vascular calcifications as a result of reduced solubility of calcium.** There is a theoretical concern from *in vitro* cell culture studies that raising extracellular pH may reduce solubility of calcium and predispose participants to vascular calcifications(26). There are currently no studies suggesting that this occurs *in vivo* with bicarbonate therapy, but this issue has not yet been addressed specifically in clinical trials. This may be more relevant to patients with advanced kidney disease and patients with Ca x Pi ratio >50, receiving phosphate binders, who are in fact prone to vascular calcification, than to population that we plan to recruit (CKD2 and 3a)(27).

- 6) Simultaneous ingestion of bicarbonate and non-absorbable antacids (aluminum and magnesium carbonate in combination with cation-exchange resins). This causes formation of easily absorbable bicarbonate in the small intestine and in this case metabolic alkalosis can occur, if bicarbonate excretion by the kidney is limited, again unlikely in participants with CKD 2 and 3a. Nevertheless, participants will be advised to avoid concomitant use of non-absorbable antacids and bicarbonate.
- 7) DXA scans. Exposure to radiation from the hip DXA (20 mRem total) for baseline and follow-up scans.

Adequacy of protection against risks

Recruitment and Informed Consent

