There is plethora of published data on use of bicarbonate supplementation and that has simplified determination of a safe dose for this study. An average dose per 85 kg patient will be ~ 25 meq/d as gel capsules containing 10 meq NaHCO₃ with sucrose in 3 daily doses; placebo capsules will contain sucrose only. Per published studies(14), each subject will be dosed to the nearest "one-half capsule" by lean body weight in kg (e.g., a 70 kg subject will receive two doses daily; capsules with half a dose can easily be prepared by our pharmacy as needed)). Participants will be monitored for evaluation of medication tolerability. Adherence to study medication will be assessed by pill count and deducted from net acid excretion measurements. Participants will be withdrawn from the study at their FV2 visit if their total carbon dioxide >30 mmol/L, their eGFR falls below 15 ml/min, they experience weight gain of more than 2 kg due to edema, develop serum potassium<3.5mmol/L, or have an increase in blood pressure (systolic or diastolic) of more than 15 mmHg (7, 15). These parameters will be assessed at each visit.

Safety measures during the assessments

All study assessments will be conducted by trained and certified staff. Safety precautions will be taken during all testing (e.g. gait speed) by applying standardized stopping criteria. If the participant reports pain, tightness or pressure in the chest, feeling faint, lightheaded or dizzy, or significant other medical problems, the test will be stopped. The PI and Co-I [name], will review lab data for medical concerns. When there are medically relevant findings, the participant will be told the cause for concern, and may be advised to consult his or her physician. If given permission by the participant, a letter will be sent to her/his primary care physician stating the concern.

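### Safety withdrawal takes participants out of the study at month 3, so no month-6 NAE/Cr is planned for them under intent-to-treat; the rule also appears in two lists that differ

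*Combined protocol and SAP*

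**What the plan says.** The withdrawal rule appears twice in the combined protocol and SAP.

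- **Safety measures during the bicarbonate intervention period:** "Participants will be withdrawn from the study at their FV2 visit if their total carbon dioxide >30 mmol/L, their eGFR falls below 15 ml/min". The sentence goes on to edema-related weight gain over 2 kg, potassium below 3.5 and a blood pressure rise over 15 mmHg. The next sentence says these parameters are checked at every visit.
- **Interventions and Interactions, bicarbonate group:** "Participants will be withdrawn if any of the following occur: total carbon dioxide >30mmol/L, serum K+ <3.5mEq/L, hospitalization for congestive heart failure". It adds the same weight and blood pressure criteria. It does not say what participants are withdrawn from.

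The schedule of events has FV1 as the 1-month call, FV2 as the 3-month clinic visit and FV3 as the 6-month clinic visit. The 4-hour urine that yields NAE/Cr is marked at BV, FV2 and FV3. Human Subjects Involvement and Characteristics instead labels month 3 as FV1 and month 6 as FV2.

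The Analytical Plan says initial analyses follow intent-to-treat. Aim 1 uses a mixed-effects ANCOVA with baseline NAE/Cr and intervention, takes a contrast at 6 months, and describes the estimate as unbiased if missingness is related to outcomes at other time points.

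**The concern.** **Main point.** Leaving the study and stopping capsules are different events, and the plan does not separate them for people who meet a withdrawal criterion. The nearest it comes is in Potential Risks: a temporary pause for intercurrent illness (item 2) and dose adjustment (item 4). Some of the criteria, such as raised total CO2 or edema, are possible effects of bicarbonate. Participants who stop for these reasons are therefore the ones whose month-6 value matters for an intent-to-treat estimate, and no collection is planned for them. What is at stake is the size of the month-6 reduction that Aim 1 sets beside its target of about 50%.

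**Secondary point.** The two lists differ in one criterion each and in timing. Heart failure hospitalization is the more consequential mismatch. The eligibility table excludes only "cardiovascular disease (Class III or IV congestive heart failure"), so milder heart failure may enter, and Potential Risks item 4 notes: "A recent study however reported slightly higher risk of heart failure in kidney patients with serum bicarbonate >24 mmol/L". Yet the dedicated safety section does not list it.

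**Working it through.** **1. Which visit is FV2?** The schedule table says month 3. The visit description agrees: at clinic visits participants "have their physical ability tested (FV2 and FV3 only"), which matches the SPPB marks at 3 and 6 months. A withdrawal rule acting at the final visit would also serve no purpose. Month 3 is the better-supported reading. Under the other label, the month-6 urine would coincide with withdrawal and no later NAE/Cr would be lost, so the main point depends on this reading and on the safety section's wording about leaving the study.

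**2. The two lists side by side**

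| Criterion | Interventions section | Safety section |
|---|---|---|
| Total CO2 >30 | yes | yes |
| K+ <3.5 | yes | yes |
| Edema weight gain >2 kg | yes | yes |
| Blood pressure rise >15 mmHg | yes | yes |
| Heart failure hospitalization | yes | no |
| eGFR <15 | no | yes |
| When it acts | any occurrence | at FV2 |

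The lowest eligible eGFR is 30 ("eGFR stage 2 (60-89) or 3 (30-59")), so eGFR <15 needs a fall of more than 1 − 15/30 = 50% and should rarely act.

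**3. The plan's own power figure.** Inputs from Sample Size: 35 per group after 12.5% loss, difference 11.4 mEq/g, two-sided 0.05. The 16.5 mEq/g is described as a within-group change but works only as an SD. A two-sample t test then gives 81.3% power, against the stated 80%, so reading 16.5 as the SD is reasonable.

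**4. Precision of the Aim 1 contrast.** SE = 16.5 × √(2/35) = 3.94 mEq/g; the 95% half-width is about 7.9.

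**5. Size of the overstatement.** Arm size is 35/0.875 = 40; planned losses are 40 × 0.125 = 5. Let a fraction k of the active arm stop at month 3 and return to baseline. The intent-to-treat effect is (1 − k) × effect. With month 6 missing, the model tends toward the full effect, so the overstatement is about k × effect. The expected effect is 20–30 (printed as meq/d, read here as mEq/g).

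| k | Overstatement (mEq/g) | Intent-to-treat effect | A 50% reduction becomes |
|---|---|---|---|
| 1/40 | 0.5–0.75 | 19.5–29.25 | 48.75% |
| 5/40 | 2.5–3.75 | 17.5–26.25 | 43.75% |

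The overstatement reaches one SE only at k = 3.94/30 = 13% to 3.94/20 = 20%. All effects in the table exceed 11.4.

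**6. Does the mixed model behave this way?** A simulation used a random-intercept ANCOVA with visit and treatment-by-visit terms, 40 per arm, change SD 16.5, correlation 0.5 (assumed), effect 25, and 5 of 40 active participants stopped after month 3 and back to baseline. The true intent-to-treat effect is 0.875 × 25 = 21.9. Over 250 runs the mean estimate was 24.9 with month-6 values missing and 21.7 with them kept (Monte Carlo SE 0.2). With 1 of 40 stopped, the gap (0.6) is close to Monte Carlo error.

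**The case against.** **On the main point.** The interventions section says only that participants are withdrawn, and this can be read as withdrawn from supplementation. The plan commits its initial analyses to intent-to-treat without defining what happens after capsules stop, and it states its missing-data condition, so the absence of post-stop data is a gap and not a contradiction. The mixed model keeps the month-3 value. The shift per participant is under 0.2 SE, and Aim 1 has no pass/fail cutoff. All of this stands, and it limits the point to the size of the estimate. It does not remove it: the stopping triggers are not in the stated model, and no on-capsule value can supply what a stopped participant's month-6 NAE/Cr would have been. For someone stopped before month 3 there may be no month-3 value at all, so the calculation above describes month-3 stops only.

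**On the lists.** They belong to one protocol and can be applied together. Parameters are assessed at every visit, and FV2 is the only clinic visit between baseline and month 6, so laboratory values, measured weight and blood pressure can be confirmed only there before the end. For month-3 chemistry the two rules agree. This also stands. What remains is an event known before FV2, chiefly a heart failure hospitalization reported at the month-1 call, which takes medical history and whose questionnaire serves "to evaluate safety and adherence and to collect 24hr-food recall data are also included".

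**A stronger reading to avoid.** A reader might infer a definite number of extra days or capsules taken under the safety-section rule. That would require staff to ignore the interventions section and take no other action, whereas the protocol provides for edema monitoring, dose adjustment and protective action after serious events. No such count is supported.

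**Conclusion.** The point holds as a follow-up gap plus a list inconsistency.

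Taking FV2 as month 3 and the safety section as worded, no month-6 NAE/Cr is planned for participants stopped on safety criteria. The Aim 1 reduction is then overstated by about k times the effect: 0.5–0.75 mEq/g per stopped active-arm participant, or 2.5–3.75 in the illustration where all 5 planned losses are such stops. Both k and full return to baseline are assumptions; partial return would give less. In both cases the overstatement is below one SE of about 3.9.

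A reader might infer that power, or the conclusion that NAE/Cr falls, is at risk. The documents do not support that: the diluted effects of 17.5–26.25 in that illustration stay well above 11.4. What shifts is the magnitude compared with about 50%.

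The list mismatch is real but partly reconcilable, and is secondary.

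**What to change.** 1. In both sections, replace withdrawal with: the participant stops study capsules and is asked to attend the remaining scheduled visits, including the month-6 4-hour urine. State in the Analytical Plan that these values enter the Aim 1 intent-to-treat model.
2. Use one six-criterion list in both sections (total CO2 >30, K+ <3.5, heart failure hospitalization, edema weight gain >2 kg, blood pressure rise >15 mmHg, eGFR <15). Apply it whenever the event becomes known and delete the tie to FV2. Apply it in both arms, in line with "The placebo group will be followed in the same manner as the bicarbonate group".
3. Housekeeping: align the visit labels in Human Subjects Involvement and Characteristics with the schedule. Also align the metabolic panel timing in the clinical assessments section, which gives baseline and 6 months and omits the month-3 draw.

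The cost is wording; no visit or test is added, because the month-6 visit and urine are already scheduled for everyone. The downside is that the Aim 1 effect may come out slightly smaller, and some who stop may decline month 6.
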